## 1.0 Background

### Ofatumumab

Ofatumumab, a novel anti-CD20 antibody, has been tested in various hematologic malignancies, and is currently FDA approved for treatment of patients with CLL that is relapsed/refractory to prior treatments with fludarabine and alemtuzumab.

Ofatumumab is a human immunoglobulin (Ig) G1k antibody which binds to a different epitope of CD20 than rituximab, a site which includes the small extracellular loop (residues 74 to 80) and the N-terminal region of the second large extracellular loop, that includes amino acids 163 and 166 (Cheson, J Clin Oncol, July 20, 2010) (Teeling JL, et al. J Immunol, 177:362-371, 2006).

Ofatumumab has been demonstrated to have greater binding avidity than rituximab and can bind closer to the cell membrane than rituximab, which may lead to be more effective complement-dependent cytotoxicity (CDC) and therefore has a potential advantage over other anti-CD20 antibodies in the setting of CLL (Teeling, 2006 and Teeling JL, et al. Blood 104:1793-1800, 2004).

### Chronic lymphocytic leukemia (CLL)

CLL is the most common form of adult leukemia in the United States. It affects males more frequently than females and affects elderly individuals with more than 50% of the patients being 70 years of age or older at the time of diagnosis. It has been estimated that there are approximately 150,000 individuals living with CLL in the United States (SEER database). The course of the disease is diverse with patients that may not require therapy for many years and eventually die of unrelated causes and patients with high risk features that survive only a few months despite treatment.

Treatment options for patients with newly diagnosed CLL in the United States consist of treatment with fludarabine as single-agent or in association with chemoimmunotherapy. In our center, frontline treatment consists of the combination of fludarabine, cyclophosphamide and rituximab (FCR) (Keating MJ, et al., J Clin Oncol, 2005, 23: 4079-4088). This combination chemoimmunotherapy has resulted in a high percentage of responses. When we reviewed our experience in elderly patients (defined as age 70 or older) treated with this combination, response rate observed in 54 patients showed an overall response rate of 80% indicating that this treatment is active. We also noted that 75% of the patients treated with this approach developed myelosuppression and were able to receive only a median of 4 out of the 6 cycles of planned chemotherapy, indicating that the FCR is poorly tolerated by older patients ([name], et al. Leuk and Lymph, 46 (Suppl.1):S86, 2005). Furthermore, the positive results with FCR have been reported in patients that are fit, have a low

number of co-morbidities and, most importantly, have a normal renal function (Hallek M, et al. Lancet 2010;376(9747):1164-1174).

### **Rationale for Use of Ofatumumab in CLL**

The rationale for evaluating the activity of ofatumumab in elderly patients with CLL is based on the experience with rituximab. Two clinical studies have been conducted at our center evaluating the activity of monotherapy with rituximab as initial treatment of patients with CLL. One study focused on the activity of rituximab in patients without indications for treatment, but with high-risk for progression based on beta2 microglobulin level. In this subset of patients the overall response (OR) rate was 82% and the duration of response was 23 months ([name] et al., Cancer 2011). In a subsequent study, we treated 32 patients age 70 or older with rituximab in association with GM-CSF. All patients had indication for treatment and patients with poor performance status were allowed to participate. In this group the OR rate was 69% and the median duration of response was 18 months ([name], et al. Leuk and Lymph, 2009). This elderly group tolerated the treatment well, with toxicity limited to infusion reactions.

Ofatumumab therefore, with its favorable toxicity profile, its clinical activity in the relapsed/refractory setting, and in vitro studies suggest that ofatumumab has greater complement-dependent cytotoxicity and antibody-dependent cellular cytotoxicity compared to rituximab, is an attractive therapeutic option for elderly patients with CLL requiring initial therapy.

## **2.0 Objectives**

### **Primary Objective:**

1.1 To evaluate the overall response rate of ofatumumab in the upfront setting in elderly, unfit patients with CLL. [Unfit patients in this trial are: patients with an ECOG/WHO performance status of 2-3 (usually defined as "slow-go or no-go") or patients with an ECOG/WHO performance status of 0-1 and a CIRS or Charlson (Charlson, 1987 J Chronic Dis 40(5): 373-83) co-morbidity score of 2 or higher.]

### **Secondary Objectives:**

- 1.2. To determine the overall survival with ofatumumab in the upfront setting in elderly, unfit CLL patients.
- 1.3. To evaluate the complete response rate and time to progression after repeated doses of ofatumumab in elderly, unfit patients with CLL.
- 1.4. To determine the plasma levels of ofatumumab in elderly, unfit patients.
- 1.5. To evaluate predictive capability of miRNAs detection in plasma samples.

### 3.0 Study Design

This is a single center open label phase II study to evaluate the efficacy and safety of ofatumumab as initial treatment of elderly, unfit patients with CLL and indications for treatment according to NCI-WG guidelines.

#### Treatment Plan:

The administration of ofatumumab will be four weekly IV infusions at the dose of 300 mg during week 1, then 2000 mg in weeks 2, 3 and 4, then monthly during months 2-12.

Pre-medication before each ofatumumab infusion must be given within 30 minutes to 2 hours prior to each treatment:

- Acetaminophen (PO) 1000 mg or equivalent
- Diphenhydramine (IV) 50 mg
- Glucocorticoid (IV) equivalent to 50 mg prednisolone. The dose of glucocorticoid can be decreased at the time of subsequent doses if grade 3 or greater infusion reaction did not occur with the preceding dose.

#### **First Infusion of 300 mg Ofatumumab:**

The initial rate of the first infusion of 300 mg ofatumumab (0.3 mg/ml) should be 12 ml/h. If no infusion reactions occur the infusion rate should be increased every 30 minutes, to a maximum of 400 ml/h, according to Table 1. If this schedule is followed, the infusion duration will be approximately 4.5 hours. If an infusion reaction develops, the infusion should be temporarily slowed or interrupted. Upon restart, the infusion rate should be half of the infusion rate at the time the infusion was paused. If, however, the infusion rate was 12 mL/hour before the pause, the infusion should be restarted at 12 mL/hour. Hereafter, the infusion rate may be increased according to the judgment of the investigator, in the manner described in this section.

#### **Subsequent infusions of 2000 mg ofatumumab:**

If the previous infusion has been completed without grade  $\geq 3$  infusion-associated AEs, the subsequent infusion of **2000** mg (2 mg/ml) can start at a rate of 25 mL/hour and should be doubled every 30 minutes up to a maximum of 400 ml/h, according to Table 2.

Duration of the infusion will be approximately 4 hours if this schedule is followed. If a Grade  $\geq 3$  AE related to the infusion occurs, the infusion must be interrupted. When the AE decreases to grade  $< 3$ , the investigator may restart the infusion.

**Table 1. Infusion rate at  
1st Ofatumumab infusion.**

Time	mL/hour
0 – 30 minutes	12
31 – 60 minutes	25
61 – 90 minutes	50
91 – 120 minutes	100
121 - 150 minutes	200
151 - 180 minutes	300
181+ minutes	400

**Table 2. Infusion rate at  
subsequent Ofatumumab infusion.**

Time	mL/hour
0 – 30 minutes	25
31 – 60 minutes	50
61 – 90 minutes	100
91 – 120 minutes	200
121+ minutes	400

During infusion the patient should be monitored closely and appropriate measurements should be performed whenever judged necessary. Allopurinol 300 mg/day will be given during the first 14 days of treatment for tumor lysis prophylaxis.

Dose Reduction: DOSE REDUCTION GUIDELINES FOR OFATUMUMAB.  
No dose reduction is planned for ofatumumab. Its administration will be held for grade 3 or higher hepatic toxicity and can be omitted if clinically indicated.

**Precautions with Ofatumumab Treatment:**

Chronic obstructive pulmonary disease, moderate to severe (unapproved use); risk of grade 3 bronchospasm during infusion. Cytopenias, including prolonged severe neutropenia and thrombocytopenia may occur; monitoring recommended.

Hepatitis B infection, carriers or at risk of infection; risk of hepatitis B reactivation with fulminant hepatitis, hepatic failure, and death; evaluate for evidence of infection before beginning treatment and closely monitor for reactivation for 6 to 12 months following therapy; discontinue therapy if viral hepatitis occurs.

Infusion reactions, some serious (e.g. bronchospasm, dyspnea, laryngeal edema, pulmonary edema, angioedema, cardiac ischemia/infarction) have been reported; especially during first 2 infusions; premedication is recommended; depending on the severity of the reaction, adjustment in infusion rate, interruption, and/or discontinuation of therapy is recommended. Obstruction of small intestinal may occur. Progressive multifocal leukoencephalopathy (PML) including fatalities, may occur; new onset or changes in preexisting neurological signs and symptoms may be indicative of PML; discontinue therapy if PML occurs.

Viral live vaccination; do not use in patients who recently received ofatumumab therapy.

**Potential Side Effects of Ofatumumab:***Common*

Dermatologic: rash (all grades, 14% to 17%; grade 3 or greater, less than 1% to 2%). Gastrointestinal: diarrhea (18% to 19%), nausea (11% to 12%). Hematologic: anemia (all grades, 16% to 17%; grade 3 or greater, 5% to 8%).

Respiratory: bronchitis (all grades, 11% to 19%; grade 3 or greater, less than 1% to 2%), cough (19%), dyspnea (all grades, 14% to 19%; grade 3 or greater, 2% to 5%), pneumonia (all grades, 23% to 25%; grade 3 or greater, 14% to 15%), upper respiratory infection (3% to 11%).

Other: fatigue (15%), Fever (all grades, 20% to 25%; grade 3 or greater, 3% to 5%)

*Serious*

Gastrointestinal: bowel obstruction.

Hematologic: neutropenia, Grade 3 or greater (42%).

Hepatic: relapsing type B viral hepatitis.

Immunologic: infectious disease (all grades, 70%; grade 3 or greater, 29%), sepsis (all grades, 8% to 10%; grade 3 or greater, 8% to 10%).

Neurologic: progressive multifocal leukoencephalopathy.

Other: complication of infusion (first infusion, 44%; second infusion, 29%).

Further information can be found in the Ofatumumab Investigator's Brochure.

### **Supplier**

GlaxoSmithKline (GSK) will supply commercial ofatumumab for this study.

### **Receipt of Study Drug**

The Investigator or designee is responsible for taking an inventory of each shipment of study drug received, and comparing it with the accompanying study drug accountability form. The Investigator or designee will verify the accuracy of the information on the form, sign and date it, retain a copy in the study file, and return a copy to GSK or its representative.

### **Storage**

The study drug will be stored refrigerated (2-8°C) in a safe and secure place. The study drug will not be frozen. A temperature log with daily readings will be kept.

### **Recommended Concomitant Therapy**

Allopurinol 300 mg/day will be given during the first 14 days of treatment for tumor lysis prophylaxis. Subjects should receive full supportive care, including transfusions of blood and blood products, antibiotics, and anti-emetics when/if appropriate. Use of filgrastim (G-CSF), erythropoietin to treat for neutropenia and anemia respectively is permitted while on study.

## **4.0 Patient Eligibility**

**Inclusion Criteria:** Patients will be eligible for inclusion in the study if they meet all of the following criteria:

- 1) Patients with chronic lymphocytic leukemia requiring treatment >65 at the time of signing informed consent.
- 2) ECOG/WHO performance status of 2-3 or patients with chronic lymphocytic leukemia requiring treatment age >65 years at the time of signing informed consent and ECOG/WHO performance status of 0-1 and a CIRS or Charlson co-morbidity score of 2 or higher.
- 3) Adequate renal and hepatic function (creatinine <2mg/dL and eGFR more than 30cc/minute, bilirubin <2mg/dL). Patients with renal or liver dysfunction due to organ infiltration by lymphocytes may be eligible after discussion with the study chairman. Patients with Gilbert's syndrome are eligible.

**Exclusion Criteria:**

1. Patients with documented prolymphocytic leukemia (prolymphocytes more than 55% in the blood).
2. Known positivity for HIV.
3. Hepatitis B (HB) defined as a positive test for HBsAg. In addition, if negative for HBsAg but HBcAb positive (regardless of HBsAb status), a HB DNA test will be performed and if positive the subject will be excluded.
4. Prior treatment for CLL.
5. Concurrent chemotherapy, radiotherapy, or immunotherapy, including other monoclonal antibodies. Localized radiotherapy to an area not compromising bone marrow function does not apply.

Patients with malignancies with indolent behavior such as prostate cancer treated with radiation or surgery can be enrolled in the study as long as they have a reasonable expectation to have been cured with the treatment modality received.

6. Any serious medical condition, laboratory abnormality, or psychiatric illness that places the subject at unacceptable risk if he/she were to participate in the study.
7. Any known hypersensitivity to ofatumumab or its components.

**5.0 Criteria for Removal from Study:**

Treatment with study drug is discontinued and the patient will be removed from study when any of the following occurs:

1. Lack of therapeutic effect.
2. Adverse event(s) that, in the judgment of the Investigator or the patient, may cause severe or permanent harm or which rule out continuation of the study drug.
3. Withdrawal of consent.
4. Lost to follow up.

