### **Evaluation During Study**

Monitoring will consist of biweekly (every other week  $\pm 3$  days) blood counts and SMA12 during treatment, then every 3 months ( $\pm 2$  weeks) during follow-up until alternative treatment for CLL or death, whichever occurs first. For patients who are HBsAg-, HBcAb+, HBsAb+/-, and HBV DNA- on enrollment and proceeded with treatment, HBV DNA PCR testing will be done every 2 months while on treatment and maintenance, then every 3 months during follow-up for 6 months.

A physician will see patients at least monthly ( $\pm 5$  days) during treatment, then every 6 months ( $\pm 2$  weeks) during follow-up. All patients will be followed for survival.

CD4+, CD8+ and peripheral blood lymphocyte subset, beta-2-microglobulin will be analyzed after month 6 and every six months thereafter. Bone marrow biopsy and aspiration will be performed as clinically indicated after month 6 and every six months thereafter.

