## **7.0 Criteria for Response**

The 2008 NCI Working Group criteria for response will be used. Response will be assessed after month 3, month 6 and every 6 months thereafter.

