### **10.0 Statistical design**

This is a phase II trial to assess the activity and tolerability of ofatumumab in elderly (age 65 or greater), unfit patients with previously untreated CLL.

Response will be assessed after month 3, month 6 and every 6 months thereafter using the 2008 NCI-WG criteria. Toxicity will be score using CTCAE v4.0. The first time point to evaluate efficacy and toxicity will be at completion of month 6 of treatment. Toxicity will be monitored during the entire treatment.

The primary endpoint of this study is OR (CR + PR) and a Simon's two-stage optimum design will be used for this study. A sample size of 34 is chosen to differentiate between a good response rate of 70% and a poor response rate of 40% with 95% power at a significance level of 0.05. The trial will stop early due to lack of efficacy if there are 6 or fewer patients with OR in the first 14 patients. Lack of efficacy will also occur if there are 18 or fewer responses in 34 patients. Secondary endpoints are progression-free survival (PFS) and CR rate. PFS is defined as time from start of therapy to death or progression of disease and it will be calculated using Kaplan Meier estimates. Responses will be assessed by Fisher's exact test with intention to treatment analysis by pre-treatment characteristics. Potential relationships between ofatumumab plasma concentrations and clinical outcomes (e.g. OR) will be explored using regression analyses.

For the correlative studies, we will assess the association between survival data and miRNA marker expression using proportional hazards models and estimate the distributions of time-to-event outcomes using the Kaplan and Meier method. We will then compare these distributions among treatment or cohort groups using the log-rank test. We will compare the proportions of complete responses between positively and negatively expressed miRNAs that are therapeutic markers in various trials. Fifty-eight samples (2-3 sequential samples from each patient) will be required to achieve 80% power at a 2-sided significance level of 0.05 and Bonferroni adjustment for testing 10 markers, assuming that 50%

patients are marker positive and that the response rates in the positively and negatively expressed markers are 75% and 25%, respectively.

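### Section 5 ends study participation when drug is stopped for lack of effect or adverse events, which contradicts the follow-up in Section 6 and could leave progression, and some responses, unassessed

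*Combined protocol and SAP*

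**What the plan says.** Section 5 joins two acts in one sentence: "Treatment with study drug is discontinued and the patient will be removed from study when any of the following occurs". Four reasons follow: lack of therapeutic effect, adverse events, withdrawal of consent, and loss to follow-up. Lack of effect is not defined and is not tied to documented progression.

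Section 6 (Evaluation During Study) describes follow-up that does not end when drug ends:

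- Blood counts and chemistry continue every 3 months "during follow-up until alternative treatment for CLL or death, whichever occurs first".
- Physician visits are at least monthly "during treatment, then every 6 months" in follow-up.
- Survival has no exception: "All patients will be followed for survival".

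Section 7 adds: "Response will be assessed after month 3, month 6 and every 6 months thereafter". It does not mention patients who are off drug.

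Two secondary aims depend on seeing progression. Section 2 includes the aim "To evaluate the complete response rate and time to progression after repeated doses of ofatumumab". Section 10 states: "PFS is defined as time from start of therapy to death or progression of disease and it will be calculated using Kaplan Meier estimates". Section 10 gives no censoring rule for patients who leave early or start other CLL treatment.

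**The concern.** Withdrawn consent and loss to follow-up properly end observation. Lack of effect and adverse events end treatment, but they are no reason to stop looking for progression. Section 5 treats all four alike, and nothing in the document reconciles it with Section 6.

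Treatment is planned through month 12 in elderly, unfit patients, so stopping for toxicity before progression is foreseeable. If those patients leave the study, their later progressions are not seen. If they are then censored at removal and their later risk differs from that of patients who stay, the Kaplan-Meier PFS curve is biased, and time to progression has the same problem. Survival follow-up recovers deaths but not missed progressions. Removal before the first assessments could also leave a patient with no response evaluation for the primary endpoint.

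**Working it through.** **1. The texts side by side**

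| Patient who stops drug for | Section 5 | Section 6 | Section 7 |
|---|---|---|---|
| Adverse event, no progression | Removed from study | Laboratory follow-up to other CLL treatment or death; visits every 6 months; survival | 6-monthly assessment, no stated end |
| Lack of effect, no documented progression | Removed from study | Same | Same |
| Documented progression | Removed from study, if judged lack of effect | Same | PFS event already recorded |
| Withdrawn consent or lost | Removed from study | Not contested | Not contested |

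The contradiction with Section 6 is direct. With Section 7 it is by implication. The first two rows are the patients affected.

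**2. The plan's own figure**

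Section 10 gives a Simon two-stage design: stop if 6 or fewer of 14 respond; lack of efficacy if 18 or fewer of 34; rates 40% and 70%; 95% power; level 0.05. The chance of passing is the sum over x = 7 to 14 of P(Bin(14, p) = x) × P(Bin(20, p) ≥ 19 − x). This gives 0.9507 at p = 0.70 and 0.0385 at p = 0.40. The design reproduces and is not in dispute.

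**3. Illustration for PFS**

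The documents give no removal rate, PFS hazard or hazard ratio, so every input except N = 34 is assumed.

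- Median PFS is 18 or 23 months. These are the durations of response to rituximab in the Section 1 rationale, used as stand-ins. For the 18-month figure: "In this group the OR rate was 69% and the median duration of response was 18 months". The 23-month figure comes from patients without indications for treatment.
- h = ln 2 / 1.5 = 0.462 or ln 2 / (23/12) = 0.362 per year.
- A share f = 0.1, 0.2 or 0.3 of patients event-free at month 6 is removed then. Event-free at month 6: 34 × exp(−0.5h) = 27.0 or 28.4, so 2.7 to 8.5 patients are removed.
- Hazard ratio after removal (HR): 0.5, 1, 2 or 3. Removed patients are censored, and nothing later is captured.

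True PFS: S(t) = (1 − f)·exp(−ht) + f·exp(−0.5h − HR·h·(t − 0.5)). The Kaplan-Meier curve with censoring at removal estimates exp(−ht).

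Example (18-month median, f = 0.2, HR 2, 24 months): Kaplan-Meier exp(−0.924) = 39.7%. True: 0.8 × 39.7% + 0.2 × exp(−0.231 − 1.386) = 31.8% + 4.0%, which is 35.7% before rounding of the parts. Overstatement: 4.0 points.

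| HR | Bias at 12 months (points) | Bias at 24 months (points) |
|---|---|---|
| 2 to 3 | +1.2 to +7.0 | +2.0 to +9.6 |
| 1 | 0 | 0 |
| 0.5 | −0.7 to −2.3 | −1.5 to −4.9 |

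Standard error of the censored estimate (Greenwood form): exp(−ht)·sqrt{[(exp(0.5h) − 1) + (exp(ht) − exp(0.5h))/(1 − f)]/34}. At 24 months with f = 0.3 it is 9.8 points (18-month median) and just under 10.0 (23-month median). The largest biases there are 8.9 and 9.6 points, both inside one standard error, and no other scenario exceeds its own. At HR 1 nothing is biased, but the standard error is 3% to 16% larger than with complete follow-up.

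**4. Illustration for the primary endpoint**

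Assume a share d is removed before any response assessment, is counted as non-responding, and would otherwise have responded at 70%. The effective rate is 0.7 × (1 − d), and the formula in step 2 gives:

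| d | Effective rate | Power |
|---|---|---|
| 5% | 0.665 | 0.895 |
| 10% | 0.630 | 0.805 |
| 15% | 0.595 | 0.679 |
| 20% | 0.560 | 0.528 |

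The documents give no value for d and do not say how an unassessed patient is counted.

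**The case against.** The strongest reply is that staff will read removal from study as coming off treatment and let Section 6 govern. Section 6 has no exception for early stoppers, and its survival sentence covers all patients. That reading is available, and under it little is lost. But the text does not say so. Section 5 is headed as criteria for removal from study, names discontinuation and removal as two things that both happen, and lists them with two reasons that do end observation.

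Three further points stand and limit the concern:

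- The document nowhere says that PFS is censored at removal. That is an inference about practice.
- The illustration assumes nothing is captured afterwards. If the survival sentence governs, deaths are known, and deaths are PFS events. Where they are entered as events for patients otherwise censored at removal, the upper figures are an upper bound on overstatement. They do not bound an analysis that keeps removed patients at risk to the date last known alive with progression unseen; the plan neither proposes nor excludes that.
- Section 6 laboratory follow-up ends at alternative CLL treatment in any case, so some patients stopped for lack of effect would leave that schedule under either reading.

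A reader might infer that overall survival is lost, or that PFS is necessarily inflated. The survival sentence protects the first unless Section 5 is taken to override it, and the direction of the second depends on an unknown hazard ratio. A reader might also infer that the primary endpoint is untouched because the two-stage rule is unchanged. The documents do not support that either, because literal removal before month 3 or 6 leaves no response assessment.

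**Conclusion.** The contradiction between Sections 5 and 6 is real and unreconciled; that with Section 7 is by implication. Read literally, Section 5 ends progression assessment in patients who stop without documented progression, so PFS and time to progression may be informatively censored, and it could leave early-removed patients without a response assessment.

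The size cannot be computed from the documents. Under the assumed values, with censoring at removal, the 24-month bias lies between about −4.9 and +9.6 points and never exceeds one standard error of the censored estimate. A reader who used the complete-follow-up standard error (8.4 to 8.6 points at 24 months) might infer that the two most extreme scenarios, 8.9 and 9.6 points, stand out from sampling noise. That is the wrong yardstick, because removal itself widens the standard error.

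This should be corrected because the loss is avoidable and missed progressions may not be recoverable. It does not invalidate the design: sample size, error rates and decision rule stand.

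**What to change.** Reconcile Section 5 with Sections 6 and 7:

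1. In Section 5, separate end of study treatment (reasons 1 and 2) from end of study follow-up (withdrawal of consent to follow-up, loss to follow-up, death). The reasons for stopping drug do not change.
2. State that patients in the first group stay on the existing Section 6 and 7 schedule for response, progression and survival.
3. In Section 10, state that stopping drug is not itself a PFS censoring event, and say how patients who start alternative CLL treatment before progression are handled.

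The cost is wording in Sections 5 and 10. No visit is added to the written schedule. If the centre had been reading Section 5 literally, these patients would keep visits that Sections 6 and 7 already describe.
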